## 5. TREATMENT OF SUBJECTS

### 5.1 Investigational product/treatment

For THA, two approaches are compared: the DAA and the PLA. Both approaches are regularly performed in hospitals and clinics in the Netherlands and in Medical Centre Alkmaar specifically. Therefore no specific surgical learning curve is expected for either of the procedures. The PLA is the most commonly used approach overall in the Netherlands.

For the DAA, the patient is placed in a supine position. The hip capsule is reached from the front, utilizing the internervous plane, located between the sartorius muscle and tensor fascia latae muscle superficially, and between the rectus femoris muscle and gluteus medius muscle more profoundly.

For the PLA, the patient is placed in the lateral position. The hip capsule is reached from the back, after incising the tensor fascia lata muscle and gluteal fascia, blunt dissection of the gluteus maximus muscle, and releasing the insertions of the piriformis, gemelli and obturator externus tendons.

For all operations the same hip prosthesis (CORAIL® Total Hip System, DePuy Synthes, Warsaw, Indiana, United States of America) will be used. All procedures will be performed using a standard operating table.

Intra- and postoperatively patients will be treated according to the standard clinical hip replacement protocol implemented in the MCA. For a detailed description of the standard postoperative pain protocol see appendix.

### 5.2 Use of co-intervention (if applicable)

Not applicable

### 5.3 Escape medication (if applicable)

Not applicable

## **6. INVESTIGATIONAL PRODUCT**

### **6.1 Name and description of investigational medicinal product(s)**

Not applicable

### **6.2 Summary of findings from non-clinical studies**

Not applicable

### **6.3 Summary of findings from clinical studies**

Not applicable

### **6.4 Summary of known and potential risks and benefits**

Not applicable

### **6.5 Description and justification of route of administration and dosage**

Not applicable

### **6.6 Dosages, dosage modifications and method of administration**

Not applicable

### **6.7 Preparation and labelling of Investigational Medicinal Product**

Not applicable

### **6.8 Drug accountability**

Not applicable

## **7. NON-INVESTIGATIONAL PRODUCT**

### **7.1 Name and description of non-investigational product(s)**

Not applicable

### **7.2 Summary of findings from non-clinical studies**

Not applicable

### **7.3 Summary of findings from clinical studies**

Not applicable

### **7.4 Summary of known and potential risks and benefits**

Not applicable

### **7.5 Description and justification of route of administration and dosage**

Not applicable

### **7.6 Dosages, dosage modifications and method of administration**

Not applicable

### **7.7 Preparation and labelling of Non Investigational Medicinal Product**

Not applicable

### **7.8 Drug accountability**

Not applicable

## 8. METHODS

### 8.1 Study parameters/endpoints

#### 8.1.1 Main study parameter/endpoint

Primary study parameters are the clinical outcome parameters:

- Hip pain and symptoms assessed using the symptoms, pain and activities of daily living (ADL) subscales of the Hip Dysfunction and Osteoarthritis Outcome Score (HOOS) after three months
- Perceived pain in the week before the moment of assessment, assessed using a Visual Analogue Scale (VAS) after three months

#### 8.1.2 Secondary study parameters/endpoints

Secondary study parameters are the clinical, functional and surgical outcome parameters and cost-effectiveness:

- Hip pain and symptoms assessed using the sports & recreation and quality of life subscales of the Hip Dysfunction and Osteoarthritis Outcome Score (HOOS)
- Length of hospital stay
- Quality of life assessed using the EQ-5D
- Functioning during daily living assessed using the HOOS
- Quality of walking assessed during a timed up and go test and a two times 50m walk using inertial sensors
- Operation time, blood loss, and other parameters of the surgical procedures
- Cup and stem positioning assessed using standard radiography
- Cost-Effectiveness assessed using the cost-questionnaire
- Muscle status assessed using MRI in a sample of 15 patients from each group
- Positioning of the implant assessed using CT scans in a sample of 15 patients from each group.
- All complications related to the surgery and rehabilitation
- Productivity costs
- Direct medical costs (costs of additional radiography, medical consumption)

#### Other study parameters

Patient characteristics such as age, gender, stature, bodyweight, side of operation (left or right), smoking.

### 8.2 Randomisation, blinding and treatment allocation

When one of the participating orthopaedic surgeons, together with the patient, decides that uncemented THA is appropriate, the patient will receive information concerning the study. After one week the patient will be called to ask whether he or she wants to participate. If the patient agrees that he or she wants to participate, signing of the informed consent and afterwards the collection of baseline measurements will take place during the next outpatient clinic visit. After receiving informed consent, the patient is included in the study and baseline measurements will be taken. After this, the patient will be randomly allocated to either the direct anterior approach (DAA) or the posterolateral approach (PLA). Randomisation will be computer-generated in Medoc Research software (SDS Medical, The Hague) with a 1:1 allocation and a block size of 10. The allocation of the patient will then be stored in the patient file and the bureau of planning is informed of the allocation to plan the surgery. After randomisation and baseline measurements have been performed, the participant is informed of being allocated to either the DAA or the PLA group, since the location of the surgical

incision makes it impossible to blind patients for group allocation. The surgeon performing the procedure will know of the treatment allocation as it is also impossible to blind the surgeon. Evaluation of radiological examinations will be done by a blinded researcher. The first 30 subjects in each groups will alternately be allocated to receive a CT or an MRI.

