### 3. STUDY DESIGN

The proposed study is a single centre (Medisch Centrum Alkmaar, MCA) parallel group randomised controlled trial, with balanced randomisation (1:1 DAA:PLA), with a follow-up of two years after surgery alongside an economic evaluation. The study will take place between 2014 and 2018 in the Medical Centre Alkmaar. The surgical procedures will be performed by three orthopaedic surgeons.

Figure 1: Flow chart of the study design

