## 4. STUDY POPULATION

### 4.1 Population (base)

Study participants are patients aged over 18 years, reporting to the outpatient department with clinical and radiographic signs of osteoarthritis of the hip. The surgeon together with the patient will decide if uncemented THA is appropriate. The study will be performed in Medical Centre Alkmaar, where in 2013 665 hip replacements were performed, of which about 80% were uncemented total hip replacements. There are currently three orthopaedic surgeons that perform both the DAA and PLA, who will participate in the current study. Each surgeon performs about 100 total hip replacements each year.

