### 10.1 Primary study parameter(s)

Continuous study parameters are described in terms of means and standard deviations if the data are normally distributed. If the data are not normally distributed then they are described in terms of median, interquartile range and minimum and maximum values. Categorical study parameters are described as proportions.

It shall be investigated if THA using DAA leads to better values of the (primary) clinical outcome parameters postoperatively and at follow-up compared to THA using PLA. In case parametric assumptions are not violated, standard parametric statistical methods will be applied (GLM (General Linear Model)), otherwise non-parametric methods will be used. The same procedure is performed for differences in changes in the primary study parameters at follow-up compared to preoperative values within one patient. Categorical outcome parameters will be analysed using Chi-square tests. If possible, 95% confidence intervals for the relevant estimates will be calculated. In addition to the univariate analyses, the longitudinal differences (effects of time) in the primary study parameters between the participants that received a THA using the DAA or PLA will be analysed in multiple regression models using random coefficient analyses. In these analyses the longitudinal differences between the two surgical procedures is studied accounting for the participation of three surgeons and possible confounding and effect modification of other determinants of the outcome parameters. The random coefficient analyses account for the dependency of the repeated measurements of the longitudinal study.

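### A single disclosed block size of 10 in an open-label, single-centre trial makes about one allocation in six predictable to someone who follows the sequence, and balance of arm by surgeon is not protected at allocation

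*Protocol*

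**What the plan says.** Protocol section 8.2 describes computer-generated randomisation "with a 1:1 allocation and a block size of 10". It mentions no varying block sizes, no restriction on who may know the block size, and no stratification factor. Section 3 describes "The proposed study is a single centre (Medisch Centrum Alkmaar, MCA) parallel group randomised controlled trial", so without strata the list is one sequence.

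Allocations are open. Section 8.2 says that the "incision makes it impossible to blind patients for group allocation", and "The surgeon performing the procedure will know of the treatment allocation as it is also impossible to blind the surgeon". Each allocation is recorded in that patient's file, and "the bureau of planning is informed of the allocation to plan the surgery". Planning of the operation therefore comes after the arm is known.

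On the surgeons, section 3 states: "The surgical procedures will be performed by three orthopaedic surgeons". Section 4.1 adds: "There are currently three orthopaedic surgeons that perform both the DAA and PLA, who will participate in the current study". Under section 8.2 a participating surgeon decides with the patient that uncemented THA is suitable. Section 11.2 lists orthopaedic surgeons, residents, nurse practitioners and physician assistants as those who include patients.

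In section 10.1, outcomes at follow-up are compared with a general linear model. The additional random coefficient models are fitted "accounting for the participation of three surgeons". The GLM comparison is not said to include surgeon.

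**The concern.** The primary endpoints (section 8.1.1) are HOOS subscales and VAS pain at three months, reported by patients who know their arm. Concealing the next allocation is one of the few protections that such a trial can still have. A block size that is constant and printed in the protocol weakens it: once one arm has used its five places, the rest of the block is known. Staff who can foresee an allocation could delay, hasten or discourage a particular patient's entry, and analysis cannot fully repair the resulting selection.

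The second issue is surgeon. The protocol treats surgeon as relevant enough to model longitudinally, but neither the randomisation nor the planning step protects the balance of arm within surgeon. If the operating surgeon is settled after the arm is known, part of a difference between surgeons could appear as a difference between approaches.

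**Working it through.** **Inputs.** Block size 10 at 1:1, so m = 5 places per arm (8.2). Total 172, that is 2 × 86 (4.4). One centre and three surgeons (3, 4.1). The target difference is 7 HOOS points (4.4). The protocol gives no figure of its own for predictability or surgeon balance, so there is none to reproduce. Its sample size is not at issue here.

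**1. Allocations certain in advance.** For a block of 2m with known history, the expected number of certain places is 2m/(m + 1) = 10/6 = 1.67, or 16.7%. Listing all C(10,5) = 252 possible blocks gives the same value. 172/10 = 17.2, so there are 17 full blocks plus two patients: 17 × 1.67 = 28.3. The first two places of a new block are never certain, so the total is about 28 of 172.

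**2. Best guessing.** If one always guesses the arm with more places left, the expected proportion correct is
[m + 2^(2m−1)/C(2m,m) − 0.5]/(2m) = [5 + 512/252 − 0.5]/10 = 6.53/10 = 65.3%, against 50% by chance. Enumeration agrees.

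**3. Is the number 10 the problem?** The certain share is 1/(m + 1): 33% for blocks of 4, 25% for 6, 20% for 8 and 16.7% for 10. A smaller fixed block would be worse. The weakness is that the size is constant and disclosed.

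**4. Chance imbalance by surgeon.** Assume equal volumes: 172/3 ≈ 57 patients each, with surgeon independent of arm. Blocking holds the arm totals near 86/86, so the number in one arm for a given surgeon is approximately hypergeometric:
SD = √(57 × 0.25 × (172 − 57)/(172 − 1)) = √(14.25 × 115/171) = 3.10.
28.5 ± 1.96 × 3.10 gives about 22 to 35. In 40,000 simulated trials with these blocks, at least one of the three surgeons reached 60/40 or worse in 15% and 65/35 or worse in 2%.

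**5. What arm-dependent booking could do.** The documents give no surgeon effect, so this is a range on assumed values. Shift in the unadjusted contrast = difference between surgeons × difference between arms in a surgeon's share of cases. With 3 HOOS points and 20 percentage points: 3 × 0.2 = 0.6. With 7 points and 50 percentage points: 7 × 0.5 = 3.5, half of the 7-point target.

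**The case against.** The figures in steps 1 and 2 need an observer who sees the whole sequence. No text gives recruiters such a list: each allocation goes to one patient's file and to the planning bureau, which section 11.2 does not name as recruiting. With three surgeons and several kinds of recruiting staff, no surgeon sees the full sequence through their own patients. Patients are called a week after receiving the information, then consent and complete baseline at the next visit before the software allocates. Steering would mean foreseeing the state of the block at a later visit while colleagues also enrol. All of this stands, and it makes 16.7% and 65% upper figures for a fully informed observer. It does not remove the risk, because staff share one centre and the block size is in the protocol.

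A reader might infer that allocations are predictable in general. They are not: about five in six are never certain, even to that observer. A reader might also infer that approach is confounded with surgeon. The documents do not support this. Section 4.1 says that all three surgeons use both approaches, and no passage assigns surgeons by arm; the possibility comes only from the order of steps and from silence. If every surgeon treats patients in both arms, a three-level surgeon term removes additive surgeon differences, and the longitudinal models already account for surgeon.

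Stratifying by surgeon is not a free remedy. It would give each surgeon a shorter list, made up of that surgeon's own patients, which is easier to follow.

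**Conclusion.** The point holds as an avoidable weakness in what section 8.2 fixes, not as an error or a contradiction. A constant, disclosed block size makes about 28 of 172 allocations knowable in advance and raises best guessing to 65%, provided that someone knows the block size and follows the entire sequence. Consent and baseline before allocation, and the interleaved sequence, reduce the practical chance of this.

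For surgeon, the supported conclusion is narrower: balance is not protected at allocation, and surgeon is named only for the supplementary longitudinal models. Chance alone would produce modest imbalance, under the assumption of equal volumes. The shift of 0.6 to 3.5 points is a what-if on assumed surgeon differences and shares, not an expected bias. The change is worth making because it is cheap and because selection at enrolment cannot be undone later.

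**What to change.** - **Section 8.2, blocks:** replace the fixed block of 10 with block sizes that vary at random, generated by the software. Keep the sizes out of the protocol and from recruiting staff. The gain comes from hiding where blocks end; small blocks would be more predictable if their sizes were known.
- **Section 8.2, surgeon:** record the intended operating surgeon before randomisation. Any later change of surgeon that depends on arm then becomes visible.
- **Section 10.1:** carry the surgeon term, already planned for the random coefficient models, into the three-month GLM comparison.
- **Optional:** stratify by intended surgeon, but only with concealed varying blocks, for the reason given under the objection.

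The cost is a software setting and a few sentences, with the sample size unchanged. The downsides are a slightly larger possible imbalance in total arm sizes and somewhat less flexible theatre planning.

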### 8.3 Study procedures

#### *Pre-operative assessment*

After inclusion participants will be asked to fill in a questionnaire. A general questionnaire containing questions about demographic characteristics of the participants, and validated questionnaires to assess clinical and functional outcomes and cost-effectiveness will be used. The Hip Dysfunction and Osteoarthritis Outcome Score (HOOS) will be used to assess pain, symptoms and function of the hip in relation to different activities of daily life. Also, a Visual Analogue Scale (VAS) will be used to assess perceived pain in the previous week. To assess quality of life, the participant will be asked to fill in the EQ-5D. A part of the questionnaire will be dedicated to questions concerning the financial costs associated with the hip problems of the participants to assess the cost-effectiveness of the approaches for hip arthroplasty. This part of the questionnaire is generally applied in cost-effectiveness studies and at some points specifically adjusted to hip problems.

In addition to the self-reported HOOS, the quality of movement and walking will be quantified to assess functional outcome. Basic balance and gait performance will be tested using the timed "up & go" (TUG) test, instrumented with inertial sensors to measure trunk accelerations, and a two times 50 meter walk at their preferred walking speed, also instrumented with inertial sensors. For the TUG test, in short, participants will be asked to stand up from a chair, walk for 3 meters, walk back to the chair and sit down on the chair. The time needed to perform the TUG as instructed will be registered. In addition, the participants will wear inertial sensors (McRoberts Dynaport Hybrid, Dimensions 87 x 45 x 14 mm, Weight 74 grams), which will be attached to the trunk using a comfortable elastic belt with Velcro fixation. The inertial sensors measure the accelerations of the trunk. Pre-operatively, standard radiographs of the pelvis (anterior posterior or AP and lateral views) are performed.

#### *Assessments during surgery and hospital stay*

Operation parameters such as operation time and blood loss will be registered. During the first 3 days after surgery, again radiographs of the pelvis will be taken from the participant as part of standard protocol. The total time of hospital stay will be registered.

#### *Follow-up assessments*

The questionnaire including the HOOS, VAS, EQ-5D and complications has to be completed by the participant at the regular follow-up visits at the orthopaedic outpatient department at 6 weeks ( $\pm 14$  days) and 12 months ( $\pm 31$  days). In addition, the participants have to fill in this

questionnaire at 3, 6 and 24 months for which the questionnaire will be sent to the participants by mail or email. Participants will be able to return the questionnaire without any costs. The questionnaire concerning the financial costs will be followed up at 3, 6, 9 and 12 months. At the regular visit to the orthopaedic outpatient department at 6 weeks, radiographs of the pelvis will be taken according to the standard protocol (AP and lateral views). In addition to standard protocol a 3D-CT scan will be performed to establish the cup and stem positioning of the hip prosthesis in a sample group. At the regular visit to the orthopaedic outpatient department at 12 months, balance and gait performance will again be tested using the TUG test and the two times 50 meter walk, both instrumented with inertial sensors. Also at 12 months radiographs of the pelvis will be made, and in a different sample group an additional MRI without contrast will be made to assess the cup and stem positioning of the prosthetic hip and the status of the hip muscles. This way patients do not need an extra outpatient clinical visit and potential end-stage tissue damage can be visualized on MRI imaging. By means of these results it is possible to analyse prosthetic positioning and muscle status against clinical results for both groups.

Table 1: Overview of the time schedule of the assessment of the study parameters

	1	2	3	4	5	6	7	8	9
Location	OC*	IC*	IC	OC	Q*	Q	Q	OC	OC
Assessment	Pre-op	Operation	Day 1-3	6 weeks	3 months	6 months	9 months	12 months	24 months
Window				± 14 days	± 31 days	± 31 days	± 31 days	± 60 days	± 60 days
Parameter									
Demographic characteristics	x								
Clinical outcome									
HOOS	x			x	x	x		x	x
VAS	x		x	x	x	x		x	x
Hospital stay			x						
EQ-5D	x			x	x	x		x	x
Complications			x	x	x	x		x	x
Functional outcome									
HOOS	x			x	x	x		x	x
Quality of walking	x			x				x	
Surgical outcome									
Operation parameters		x							
Pelvic radiography	x		x	x				x	
CT (sample group)				x					
MRI (sample group)								x	
Economic parameters	x				x	x	x	x	

\*OC: Outpatient Clinic; C: Inpatient Clinic; Q: Questionnaire sent to patient

## **8.4 Withdrawal of individual subjects**

Withdrawal is not to be expected, as a standard implant is being used and follow-up is close to routine follow-up of total hip arthroplasty following the protocol of the Medical Centre Alkmaar. Participants can stop participating in the study at any time for any reason if they wish to do so without any consequences. Patients who withdraw from the study will have the reason for their withdrawal recorded, if given, on the case report forms (CRF's). The postoperative assessments include standard evaluations according to the clinical protocol, so every attempt must be made to ensure that all the participants return for these controls. The researchers and/or the treating specialist involved can decide to withdraw a participant from the study for urgent medical reasons.

### **8.4.1 Specific criteria for withdrawal**

Not applicable

## **8.5 Replacement of individual subjects after withdrawal**

If a participant withdraws from the study, he/she will not be replaced.

## **8.6 Follow-up of subjects withdrawn from treatment**

Participants who stop participating but do not withdraw their consent will be followed according to the standard clinical protocol currently used for patients with a total hip arthroplasty for recording of any adverse events. The patient shall not be asked to perform study related activities. It will be noted in the patient file if the patient no longer wishes to participate or if the patient has withdrawn informed consent.

## **8.7 Premature termination of the study**

If the research team has signals that one of the approaches for hip arthroplasty is associated with a significant complication rate, a preliminary analysis will be performed. Since both procedures are already performed as standard procedures in the MCA it is not expected that the complication rate in one of both procedures will exceed the current registered rate. In 2012 550 primary total hip arthroplasties were performed in the MCA. At the time of writing this protocol, complications were registered for 395 patients, of whom 8 (2,0%) had a complication of any kind. When 86 patients are included the amount of complications shall be compared to 2012. If, against expectations, the complication rate of luxations and/or infections per subgroup is more than twice the total complication rate of 2012 or the complication rate for both groups combined is more than twice the rate of 2012 (4%) we shall abort the trial format. Furthermore, odds ratios will be calculated for the major complications, such as dislocation or infection, in both groups. In case of a significant difference of the odd ratio from one, the randomisation will be ended.

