#### 9.2.2 Serious adverse events (SAEs)

A serious adverse event is any untoward medical occurrence or effect that at any dose:

- results in death;
- is life threatening (at the time of the event);
- requires hospitalisation or prolongation of existing inpatients' hospitalisation;
- results in persistent or significant disability or incapacity;
- is a congenital anomaly or birth defect;
- Any other important medical event that may not result in death, be life threatening, or require hospitalization, may be considered a serious adverse experience when, based upon appropriate medical judgement, the event may jeopardise the subject or may require an intervention to prevent one of the outcomes listed above.

The sponsor will report the SAEs through the web portal *ToetsingOnline* to the accredited METC that approved the protocol, within 15 days after the sponsor has first knowledge of the serious adverse events. SAEs that result in death or are life threatening should be reported expedited. The expedited reporting will occur not later than 7 days after the responsible investigator has first knowledge of the adverse reaction. This is for a preliminary report with another 8 days for completion of the report.

If prolongation of hospital stay is due to logistical reasons (e.g. a patient is placed on a waiting list for a place in a rehabilitation centre), it will not be reported as an SAE. Prolongation of hospital stay or re-hospitalizations due to infection or luxation of the hip prosthesis are considered a standard risk in THA. In addition, a retrospective analysis in the Medical Centre Alkmaar (see introduction section) showed no differences in the occurrence of these events between DAA and PLA. Therefore they will not be reported as an SAE.

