**10.4 Interim analysis (if applicable)**

Not applicable

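### The halfway abort rule fires on two luxations or infections in one arm; its chance of a false abort (about 12% to 38%) is unstated, and its benchmark, denominator and test are not properly fixed

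*Protocol*

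**What the plan says.** Section 8.7 takes its reference from the hospital's own 2012 series. "In 2012 550 primary total hip arthroplasties were performed in the MCA", and "complications were registered for 395 patients, of whom 8 (2,0%) had a complication of any kind". The timing is set by "When 86 patients are included the amount of complications shall be compared to 2012". Two criteria then lead to a mandatory abort: an arm-level one, met if "the complication rate of luxations and/or infections per subgroup is more than twice the total complication rate of 2012", and an overall one, met if "the complication rate for both groups combined is more than twice the rate of 2012 (4%) we shall abort the trial format". A third criterion compares the arms on major complications through odds ratios: "In case of a significant difference of the odd ratio from one, the randomisation will be ended".

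Other sections bear on this:

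- Section 4.4 plans 172 patients, so 86 is halfway.
- Section 8.2 allocates 1:1 in blocks of 10, and places inclusion after consent but before randomisation and surgery.
- Section 10.1 names chi-square tests for categorical outcomes.
- Section 10.4 marks interim analysis as not applicable.
- Section 9.2.2 says of hospital stays prolonged, or readmissions caused, by infection or luxation: "Therefore they will not be reported as an SAE".
- Section 9.5 provides no DSMB.

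**The concern.** The rule is binding and can end the trial at half size, but it is written as a percentage of small numbers. In arms of about 43, a limit near 4% lies between one event and two. The protocol does not say how often it would be crossed if neither approach were worse than 2012 practice.

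Four further points make the rule hard to apply or interpret. The arm criterion counts luxations and infections but compares them with complications of every kind. The trigger for the look counts patients who may not yet have been operated on. The odds-ratio criterion has no test or significance level. And the section on interim analysis denies that such a look exists.

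At stake is the primary comparison. Section 4.4 sizes the trial at 72 per group for 7 HOOS points with SD 15. If enrolment stopped with 43 per arm and nobody dropped out, the standardised difference would be 7 / (15 × √(2/43)) = 2.16. Power would be about Φ(2.16 − 1.96) = 58%, against the planned 80%.

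**Working it through.** **Inputs.** Benchmark 8/395, any complication (8.7); look at 86 included (8.7); 1:1 allocation (8.2), so about 43 per arm. The 2012 luxation/infection rate is not given, so I vary it from 0.5% to 2%. I read a subgroup as a treatment arm, and assume all 86 patients are operated and observed.

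**The plan's own figures.** 8/395 = 2.03% and 2 × 8/395 = 4.05%, which agree with the stated 2.0% and 4%. The exact 95% interval for 8/395 is 0.9% to 4.0%, so the limit sits at the upper end of the benchmark's own sampling error.

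**Trigger in events.**
- One arm: 1/43 = 2.3% and 2/43 = 4.65%, so two events. The same holds for arms of 41 to 45.
- Both arms: 3/86 = 3.5% and 4/86 = 4.65%, so four events.

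**False-abort probability.** Let q be the luxation/infection rate and 2% the rate of any complication, equal in both arms. For one arm, P(X ≥ 2) = 1 − (1−q)^43 − 43q(1−q)^42; for either arm, 1 − (1 − P)². The full rule adds four or more complications overall. It is 1 minus the summed trinomial probability of at most one luxation/infection in each arm and at most three complications in total.

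| q | one given arm | either arm | full rule |
|---|---|---|---|
| 0.5% | 2.0% | 3.9% | 11.6% |
| 1.0% | 6.9% | 13.3% | 17.5% |
| 1.5% | 13.6% | 25.4% | 26.5% |
| 2.0% | 21.2% | 38.0% | 38.0% |

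The overall criterion alone, P(X ≥ 4 of 86) at 2%, is 9.4%. In the last row it adds nothing, because four luxations/infections across two arms always put at least two in one arm.

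**Effect of the benchmark mismatch.** Luxations and infections are a subset of all complications, so doubling the any-complication rate gives the arm criterion a limit at least as high as a matched one. If the matched 2012 rate were 1%, doubling would give 2%. One event (1/43 = 2.3%) would exceed it, and the chance of at least one event in either arm would be 1 − 0.99^86 = 58%.

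**Denominator.** If the rate is taken among included patients, those not yet operated on dilute it. If it is taken among operated patients, one event exceeds the limit in any arm with 24 or fewer operated (1/24 = 4.2%).

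**Odds-ratio trigger at 43 v 43, two-sided 5% assumed.**
- Chi-square without continuity correction: 4 v 0 gives 86 × (4 × 43)² / (43 × 43 × 4 × 82) = 4.19, p = 0.041; 3 v 0 gives p = 0.078. So 4 v 0 is needed, and power for 2% v 8% is 24%.
- Fisher's exact test: 5 v 0 gives p = 0.055 and 6 v 0 gives p = 0.026. So 6 v 0 is needed, and power is 6%.

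**Would a real excess be missed?** With 2% v 8% luxation/infection, the arm criterion fires in the worse arm with probability 86.9%. In at least one arm it fires with probability 1 − (1 − 0.869)(1 − 0.212) = 90%.

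**The case against.** The strongest defence is that a cautious trip-wire suits a surgical trial without a DSMB, and that how many false alarms to tolerate is for the sponsor to judge. That stands as far as the choice of threshold goes. It does not excuse a binding rule whose error probability is unstated and whose denominator and test are undefined.

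Four stronger readings are tempting and are not supported.

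- *An abort by chance is likely.* The highest figure at an unchanged 2% is 38%, below one half. It requires every 2012 complication to have been a luxation or infection.
- *The mismatched benchmark adds to the false-abort risk.* It works the other way: it makes the arm criterion more lenient than a matched one with the same doubling.
- *The odds-ratio trigger is nearly inert, so real harm would pass unnoticed.* The 6% power rests on Fisher's test, which the protocol does not name. The chi-square test of section 10.1 gives 24%, and the arm criterion would catch a 2% v 8% excess about 90% of the time.
- *The SAE exemption, with no DSMB, hides these events.* Section 9.2.1 records all adverse events, and Table 1 schedules complications from the first postoperative days to 24 months. Section 9.1 requires the METC to be told if disadvantages exceed those foreseen, and section 12.4 adds annual reporting. The exemption does not stop section 8.7 from working.

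A reader might also expect trial follow-up to find more complications than the 2012 register did. The protocol does not describe how that register was filled, so I do not rely on this.

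**Conclusion.** The point holds as a fault of over-triggering and incomplete specification. At the planned look, two luxations/infections in one arm or four complications overall force an abort. With nothing changed from 2012 this happens with probability of about 12% to 38%, depending on a rate the protocol does not give. The range assumes 2% any complication in both arms, independent patients, 43 per arm, and all 86 operated and observed. It does not allow for the sampling error in 8/395.

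The arm criterion's benchmark is of a different event class, and comes from 395 of 550 procedures with no stated follow-up window. Since it errs on the lenient side, it cannot be corrected without also revisiting the threshold. The conflict between sections 8.7 and 10.4 is plain on the page. The documents do not support a claim that the plan would fail to detect a large difference between arms.

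**What to change.** Amend section 8.7 as follows:

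- State each criterion as a number of events among operated patients who have reached a defined minimum follow-up.
- Use the same event class in the trial and in 2012: luxation plus infection for the arm criterion, any complication for the combined one. Give the 2012 count for each.
- Reset benchmark and threshold together. The sponsor chooses the counts from an exact binomial calculation and states the false-stop probability. The chance of stopping under a real excess belongs beside it, because higher counts reduce both.
- Name the test and significance level for the odds ratio.

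Replace the entry in section 10.4 with a reference to this look. Reconcile sections 8.7 and 9.2.2 on how luxations and infections are reported.

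The cost is a protocol amendment and a slightly later look, since operated patients with follow-up accrue after inclusion. No extra patients or visits are needed.
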